According to the CDC MACDP, the prevalence of MCMs for mothers <25 years of age in the US is 2.54% (Correa, 2007). According to the CDC National Vital Statistics System (NVSS), the prevalence of preterm birth and LBW for mothers <25 years of age are 11.71% and 8.50%, respectively (Martin, 2015).

The table below depicts sample sizes of 5, 20, 50, 100, and 150 live births and the associated effect sizes (i.e., the ratio of the registry-derived prevalence versus the reference prevalence) that would be detectable using a binomial distribution, a power of 80%, and a 1-sided Type I (false positive) error rate of 5% (Altman, 1991). For example, with a sample size of 100 live births, the study will have 80% power to detect a 1.79-fold

increase in the prevalence of preterm birth compared with the reference of 11.71% (population prevalence). In other words, if the registry-derived prevalence estimate is at least 1.79 times higher than the reference prevalence of preterm birth, the 1-sided 95% confidence interval for the estimate will exclude 11.71% (i.e., will lie above 11.71%), with a probability of 80%.

Table 9.5-1 Detectable effect size assuming 80% power

Sample size (N of live births)	Effect size (ratio of the registry-derived prevalence versus the reference prevalence for mothers <25 years of age)		
	MCM [reference = 2.54%]	PTB [reference = 11.71%]	LBW [reference = 8.50%]
5	19.30	5.75	7.92
20	7.95	3.13	3.69
50	4.23	2.24	2.59
100	3.07	1.79	1.96
150	2.66	1.63	1.82

Abbreviations: LBW = low birth weight; MCM = major congenital malformations; PTB = preterm birth.

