9.6.2 Software and Hardware

Power calculations presented in this protocol were conducted using SAS statistical software and a 1-sample binomial distribution with a 1-sided Type I error rate of 5%. Data analyses will be performed similarly using SAS (version 9.2 or higher; SAS Institute, Cary, NC).

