The primary population for analysis will include prospective evaluable participants exposed to BEXSERO that are not lost to follow-up (i.e., participants with appropriate outcome information that meet the minimum criteria for evaluation). Because early prenatal testing is so frequent, it may be difficult to achieve adequate numbers of prospectively identified pregnant women if all pregnancies with prior prenatal testing are excluded from the analysis. Therefore, the primary analysis will include pregnancies enrolled prior to outcome but after prenatal testing as long as the test does not indicate the presence of an abnormality.

Exclusions for Analysis Purposes

Invalid registry reports and pregnancies deemed lost to follow-up will be excluded from the primary analysis. Retrospective reports will not be included, although retrospective

cases with MCMs will be reviewed and reported separately for signal detection purposes. In the event that it cannot be ascertained to which meningococcal B vaccine the woman was exposed, an unknown exposure cohort will be established and analyzed separately.

Sequential Pregnancies

The number and outcome of sequential pregnancies will be noted and presented. Sequential pregnancies will be included in the analytic dataset.

Multiple Gestation Pregnancies

The number, type (e.g., twin, triplet), and outcome of multiple gestation pregnancies will be noted and presented. Multiple gestation pregnancies will be included in the analytic dataset.

General Considerations for Data Analyses

This study is observational, and epidemiological methods will be employed for data collection and analyses.

Descriptive analysis will be performed for all prospective, evaluable data. The summary statistics for continuous and categorical variables to be used will be specified in the statistical analysis plan (SAP) but may include means, standard deviations, medians, minimums, maximums, percentiles, frequencies, and percentages. For analyses of associations between pregnancy outcomes and BEXSERO exposure, confounding and effect modification will be evaluated descriptively.

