9.7.3 Statistical Methods

Overall and stratum-specific point estimates and 95% confidence intervals will be calculated using the binomial distribution for prevalence estimates of MCMs, preterm birth, and LBW among pregnant women exposed to BEXSERO and their live births. For each prevalence estimate, both 1-sided and 2-sided 95% confidence intervals will be calculated and reported. One-sided confidence intervals are appropriate as we are specifically interested in detecting outcome prevalence estimates greater than their respective reference prevalence, and 2-sided confidence intervals will provide further description of the accuracy of the estimates.

Because most structural defects have their origins in the first trimester of pregnancy during the period of organogenesis, analyses of MCM will be stratified by trimester of exposure, if applicable. It is expected that the vast majority (99%) of prenatal exposures will occur during the first trimester before the pregnancy is recognized. The prevalence of combined MCMs reported to the registry will be calculated as a proportion with the number of MCMs as the numerator and the number of live births as the denominator. Pregnancy losses with reported MCMs occurring at or after 20 weeks' gestation will be included in the numerator of the estimate of risk for MCMs to increase sensitivity and to allow comparison of outcomes with the CDC MACDP, which calculates prevalence by this convention. A secondary analysis will be conducted including pregnancy losses with reported MCMs occurring at less than 20 weeks' gestation. The prevalence of combined MCMs in exposed cases will be compared with that of the CDC MACDP (Correa, 2007).

Only cases meeting the CDC MACDP criteria for a defect or with 2 or more conditional defects will be included in the primary analysis. Single minor defects do not constitute a MCM according to the CDC MACDP classification; therefore, they will be listed in the report, but not included in the primary analysis.

The prevalence of preterm births and LBW will be calculated as proportions, with the number of live births as the denominator. These prevalence estimates in exposed cases will be compared with those of the CDC NVSS (Martin, 2015). Because MCMs are often associated with preterm birth and LBW, sensitivity analyses will be performed excluding infants with MCMs from the numerator and denominator when prevalence estimates are determined for these outcomes.

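### Preterm-birth and low-birth-weight intervals treat co-twins as independent, so they are slightly too narrow and a borderline signal can rest on one twin pair

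*Combined protocol and SAP*

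**What the plan says.** Under Multiple Gestation Pregnancies, section 9.7 of the protocol states: "Multiple gestation pregnancies will be included in the analytic dataset". Apart from that, the number, type and outcome of such pregnancies are only to be presented. The preceding paragraph adds: "Sequential pregnancies will be included in the analytic dataset".

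Section 9.3.3 defines a live birth as an infant. The formulas in section 9.7.3 put live births in the denominator for both preterm birth and LBW. The general text in section 9.7 allows either women or live births as a denominator, but the formulas settle it for these two outcomes. On intervals, section 9.7.3 says: "Overall and stratum-specific point estimates and 95% confidence intervals will be calculated using the binomial distribution".

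The planning in section 9.5 uses the same unit, "sample sizes of 5, 20, 50, 100, and 150 live births", and treats a one-sided 95% interval lying above the reference as detection. The references are stated as: "the prevalence of preterm birth and LBW for mothers <25 years of age are 11.71% and 8.50%, respectively".

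No section gives a clustered variance, a design effect, a one-infant-per-pregnancy rule or a singleton-only analysis. The only sensitivity analysis specific to preterm birth and LBW removes infants with malformations. Several details are deferred to a SAP, but within-pregnancy correlation is not among them.

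**The concern.** A binomial variance is right only if infants are independent. Twins leave the uterus together, so preterm birth is close to an all-or-none outcome for the pair, and their birth weights are correlated. Counting them as two independent infants understates the variance.

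The registry plans for 5 to 150 live births and reads a signal from whether the lower limit clears a fixed reference. At that size one preterm pair adds two events at once. A reader could then see a signal without knowing that a single delivery carried it over the line.

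**Working it through.** **1. Reproduce the plan's figure.** Inputs from sections 9.5 and 9.6.2: exact one-sample binomial, one-sided 5%, power 80%, p0 = 0.1171. Take the smallest r with P(X ≥ r | N, p0) ≤ 0.05, then solve P(X ≥ r | N, p1) = 0.80.
- Preterm birth, N = 100: r = 18, attained error 0.0418, p1/p0 = 1.789. The plan says "with a sample size of 100 live births, the study will have 80% power to detect a 1.79-fold" increase.
- LBW, N = 100: r = 14, attained error 0.0437, ratio 1.961 (table: 1.96).

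The whole table reproduces to rounding with independent infants, so it contains no allowance for twins.

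**2. Assumptions (none is in the documents).** Share of infants who are twins f = 2–3%; twin risk p_t = 40–55%. For preterm birth both twins share the outcome (100%). For LBW, among pairs with any LBW infant, 70% have both. Overall prevalence p equals the reference.

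**3. Design effect.** With P11 the probability that both twins are affected,

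Deff = 1 + f × (P11 − 2·p·p_t + p²) / [p(1 − p)].

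- Preterm birth: P11 = p_t and p(1 − p) = 0.1034. For p_t = 0.40 the bracket is 0.400 − 0.0937 + 0.0137 = 0.320, so Deff = 1.062 (f = 2%) to 1.093 (f = 3%). For p_t = 0.55 it is 0.435, giving 1.084 to 1.126.
- LBW: 70% concordance means P11/(2p_t − P11) = 0.7, so P11 = 0.8235·p_t; p(1 − p) = 0.0778. For p_t = 0.40 the bracket is 0.269, giving 1.069 to 1.104. For p_t = 0.55 it is 0.367, giving 1.094 to 1.141.

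The range is therefore 1.06–1.14. Since √1.06 = 1.03 and √1.14 = 1.07, correct intervals are about 3–7% wider.

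**4. Average false-signal rate.** Simulating the exact rule with these inputs (400,000 registries per scenario; N = 20, 50, 100, 150) gives 2.7–5.4% for preterm birth and 2.8–5.5% for LBW. For preterm birth at N = 100 it is 4.7–5.2%, against 4.2% under independence.

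**5. What one pair does.** Suppose 100 infants include one pair, both preterm, and the other 98 are at the reference rate. A signal then needs at least 16 events in 98: P(X ≥ 16 | 98, 0.1171) = 10.6%, against 4.2% for 100 independent infants. This is conditional on the pair being preterm and is not the procedure's overall error. Under independence both members of a pair would be preterm with probability 0.1171² = 1.4%. Under the assumptions it is 40–55%.

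**6. The borderline count.** One-sided exact lower limits at N = 100 are 11.13% for 17 events and 11.97% for 18, against 11.71%. Dividing events and infants by the design effect, 18/100 gives 11.83% at 1.05, 11.72% at 1.09 and 11.62% at 1.13. The limit reaches the reference at about 1.094.

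If those 18 events include one preterm pair and there are no other multiples:
- singletons only: 16/98, lower limit 10.52%;
- one infant per pregnancy: 17/99, lower limit 11.25%.

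Either analysis shows that the signal depended on the pair.

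**The case against.** The strongest counter-case is that this barely matters. Few pairs are expected: at 3% twin infants, 0.03 × 100/2 = 1.5 pairs among 100 infants, with a 0.97^50 = 22% chance of none. At N = 20 it is 0.3 pairs and 74%. The discreteness of the exact binomial absorbs most of the extra variance. The registry is declared descriptive, multiple gestations will be presented, and section 9.9 promises that intervals will be examined for random variability. An attentive reader could spot a twin pair behind a signal.

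Most of that stands, and it limits the point. A reader might infer that the nominal 5% false-signal rate is broken. The documents do not support that: on plausible inputs the average rate stays close to or below 5%. Larger inflation needs a much higher twin share, for which the documents give no basis. For example, 10% twin infants at 55% risk with the overall rate held at the reference forces singleton preterm risk down to (0.1171 − 0.055)/0.90 = 6.9%. Nor does the 18/100 signal generally vanish after adjustment: it survives at a design effect of 1.09, and at 19/100 the limit is still 12.45% at 1.13.

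The counter-case does not show that the plan handles the borderline case. Presenting the number of multiples does not commit the analyst to re-estimating without them. Section 9.7.3 also does not say which binomial interval will be reported. The exact method is inferred from the sample-size table.

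**Conclusion.** The point holds as a minor one. As written, the plan counts co-twins as independent, and its preterm-birth and LBW intervals are somewhat too narrow: about 3–7% on the assumptions in step 2, all of which come from outside the documents. The average false-signal rate is not materially affected if the intervals are exact. The practical exposure is a count at or just above the threshold, where one twin pair can decide whether a signal is declared.

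The same reasoning applies to sequential pregnancies of one woman, but a mother-level method would not fully cover them. Section 9.7 acknowledges that de-identified reports lack identifying information, so two pregnancies of one mother may not be linkable.

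The documents do not say whether the reference prevalences include multiple births. If the multiple-birth share differs between registry and reference, the point estimates shift too, which is a further reason to show singleton results.

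**What to change.** Add to section 9.7.3 a sensitivity analysis of preterm birth and LBW restricted to singletons (or to one infant per pregnancy, with the selection rule fixed in advance), using exact binomial intervals and compared with a singleton reference where one is available. Require the report to state whether any signal depends on a multiple gestation. Name the exact method for the main intervals as well.

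Where there are enough multiples to estimate it, also report an interval clustered on the mother. With the zero to two pairs expected at most planned sizes an estimated design effect would be unstable, so this should be conditional and not the main remedy.

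The cost is a few lines of analysis text. Section 9.7 already has the number and type of multiple gestations recorded, and section 10 assigns mother and infant identifiers, so no new data are needed. The sensitivity analysis will have slightly fewer infants and slightly wider intervals.

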8. RESEARCH QUESTION AND OBJECTIVES

The objective of the BEXSERO Pregnancy Registry is to evaluate pregnancy outcomes among women immunized with the BEXSERO vaccine within 30 days prior to the LMP or at any time during pregnancy. The primary outcomes of interest include major congenital malformations (MCMs), preterm birth, and low birth weight (LBW).

Other pregnancy outcomes will be collected, including stillbirths and spontaneous abortions (SABs). The probability of SAB varies greatly as a function of when the pregnancy is enrolled in the registry ([Savitz, 2002](#)). Because pregnancies will be reported to the registry at different and imprecise times during gestation, calculation of the prevalence of SAB from the registry is deemed inappropriate and could lead to erroneous conclusions. For example, if a woman enrolls in the registry at 16 weeks of pregnancy, only an SAB after this time could be detected and included in prospective reports. Similarly, SABs occurring earlier in gestation may not have been recognized and/or reported.

This registry is primarily descriptive and designed to detect potential safety signals rather than test hypotheses.

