9.5 Study Size

The pregnancy registry is a PMC agreed upon with the CBER to commence enrolment on 31 January 2016 and to continue for a period of 3 years or pending CBER review and discussion of results with GSK. will submit a full study report to CBER by 31 May 2020.

The registry will prospectively enroll women with confirmed or possible (i.e. if the brand is unknown) exposure to BEXSERO 30 days prior to LMP or at any time during pregnancy. BEXSERO is not contraindicated during pregnancy, but should be used during pregnancy only if clearly needed. Under the current ACIP recommendations, the CDC estimates 350,000 individuals will be advised to receive a meningococcal B vaccine (MacNeil, 2015), of whom it is likely that a small proportion will be exposed during pregnancy. There are uncertainties regarding the degree of market penetration and vaccine uptake that will be achieved in at-risk groups. A recent US study of the safety of Cervarix[®] in pregnancy was terminated due to low accrual of subjects attributed to low uptake of the vaccine in the US (GSK, 2015). To account for this, and that the proportion of clinically recognized pregnancies that can be expected to result in a live birth is approximately 62% (Martin, 2015), a range of sample size estimates was considered, from a minimum of 5 to 150 live births.

It is likely that the majority of exposures (99%) will be the result of inadvertent exposure within 30 days prior to LMP or early in the first trimester before pregnancy status is known. If exposures occur later in pregnancy, results will be stratified by trimester of exposure, acknowledging that the power of stratified analyses to detect statistically significant differences will be limited by the sample size of each subgroup.

The expected low frequency of BEXSERO exposure in pregnancy will limit the statistical power of this study. As the sample size of the study increases, there will be a corresponding increase in the power of the study to detect increases in the prevalence of outcomes. The study will have greater power to detect prevalence increases for relatively common outcomes (with higher prevalence) but will have less power to for more uncommon outcomes, such as MCM.

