9.7 Data Analysis

Registry Case Management and Disposition

Prospective Registry Reports

The registry will encourage prospective registration, which is defined as registration of a pregnancy exposure prior to knowledge or perceived knowledge of the pregnancy outcome (e.g., structural defect or genetic abnormality noted on a prenatal test). Those with no abnormalities identified on a prenatal test prior to enrollment will be considered prospective and included in the analysis. The rationale, potential bias, and analytic techniques to address any bias that may be introduced by this practice are addressed in [Section 9.7.4](#).

Data from HCP networks and HMOs that provide de-identified data on all exposed pregnancies in their network will fall into the category of prospective registry reports, as these networks/HMOs provide objective data on every pregnancy exposure in the network/HMO, both positive and negative outcomes. Thus, they avoid the reporting bias inherent in retrospective reporting only after a negative outcome has been noted.

Retrospective Registry Reports

Retrospective reports will also include subjects for whom the pregnancy outcome has already occurred or an abnormality has been identified on a diagnostic or screening prenatal test prior to enrollment. Retrospective reports can be biased toward the reporting of more unusual and severe cases and are less likely to be representative of the general population experience than reports reported prior to knowledge of outcome. Therefore, retrospective reports will not be included in the primary analysis and statistical calculations. Retrospective reports with reported MCMs and/or spontaneous fetal losses will be reviewed to aid in detection of early signals and listed in registry reports. Retrospective reports will not be actively solicited by the registry and will not be captured in the registry database unless a congenital anomaly is reported.

Loss to Follow-up

For a prospective report or pregnancy where follow-up information on the pregnancy outcome (live birth, fetal loss, etc.) is never obtained or is unavailable, the pregnancy will be considered lost to follow-up. Subjects lost prior to pregnancy outcome will be tallied in the registry reports but not included in the statistical analyses.

Duplicate Registry Reports

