The registry will identify the number of cases for the primary outcomes of MCM, preterm birth, LBW, and in addition for second trimester SABs; prevalence estimates will be calculated as proportions of these outcomes from the total number of pregnant women or live births, or in the case of second trimester SABs, the subset of women exposed prior to the 20th week of gestation. For each prevalence estimate, both 1-sided and 2-sided 95% confidence intervals will be calculated and reported. One-sided confidence intervals are appropriate as we are specifically interested in detecting outcome prevalence estimates greater than their respective reference prevalence, and 2-sided confidence intervals will provide further description of the accuracy of the estimates.

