9.7.1 Statistical Hypotheses

This registry is primarily descriptive and designed to detect potential safety signals, rather than test hypotheses. We are specifically interested in detecting whether the prevalence estimates of MCM, preterm birth, and LBW among the live births of pregnant women

exposed to BEXSERO are greater than the prevalence of these outcomes among the general population.

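### Section 9.7 plans a second-trimester SAB prevalence that Section 8 calls inappropriate, with a denominator set by week of exposure and not by week of enrolment

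*Combined protocol and SAP*

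**What the plan says.** Section 8 collects SABs but states that "calculation of the prevalence of SAB from the registry is deemed inappropriate and could lead to erroneous conclusions". The reason given is that women register at varying and imprecise points in gestation. The example is a woman who enrols at 16 weeks, for whom "only an SAB after this time could be detected and included in prospective reports". No trimester is exempted.

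Section 9.7 (General Considerations for Data Analyses) adds second-trimester SABs to the outcomes for which a prevalence is calculated. The denominator is "in the case of second trimester SABs, the subset of women exposed prior to the 20th week of gestation". Every prevalence gets a 1-sided and a 2-sided 95% interval, and the 1-sided one is justified because the registry is "interested in detecting outcome prevalence estimates greater than their respective reference prevalence".

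Other relevant text:

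- **Exposure timing (Section 9.5):** "It is likely that the majority of exposures (99%) will be the result of inadvertent exposure within 30 days prior to LMP". The same sentence adds exposures soon after conception, while the pregnancy is still unrecognised.
- **Retrospective reports (Section 9.7):** these include "subjects for whom the pregnancy outcome has already occurred" before enrolment, and they are kept out of the statistical calculations.
- **Networks and HMOs (Section 9.7):** those that "provide de-identified data on all exposed pregnancies in their network will fall into the category of prospective registry reports".
- **Aims (Section 9.7.1):** "We are specifically interested in detecting whether the prevalence estimates of MCM, preterm birth, and LBW"; SAB is not listed.

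**The concern.** The protocol gives two instructions that cannot both be followed, and the Section 9.7 denominator does not repair the problem that Section 8 describes. That problem is delayed entry: a woman can be seen to have an SAB only after she enrols. A condition on week of exposure does not address it.

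The resulting proportion has no stated target risk. Printed with confidence intervals, it invites comparison with an outside SAB rate, which is the error Section 8 warns against. The 1-sided interval presupposes a reference prevalence, but reference values are given only for major congenital malformation (MCM), preterm birth and low birth weight (LBW).

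**Working it through.** **No SAB figure to reproduce.** The protocol gives no reference prevalence, power or sample size for SAB. Table 9.5-1 covers only MCM, preterm birth and LBW. It reproduces by exact binomial calculation (preterm birth, 100 live births: 1.789 against the stated 1.79) and has no bearing on this point.

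**Who is in the denominator.** SAB ends before week 20 (Section 9.3.3) and the second trimester starts at week 14 (Sections 9.4.1 and 9.7.3). The exposure condition can remove only the roughly 1% or fewer exposed later. The primary population admits any pregnancy enrolled before its outcome (Section 9.7, Analysis Population). On the consented routes (self-enrolled or enrolled by the provider):

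- enrolled at week 20 or later: counted, cannot be a case;
- enrolled within weeks 14 to 19: counted, observed for part of the window;
- enrolled early, pregnancy ends before week 14: counted, cannot be a case;
- lost before enrolment: retrospective, so not counted.

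**Direction.** Let q be the risk of loss in weeks 14 to 19 among pregnancies ongoing at week 14, and f the share lost in weeks 4 to 13.

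- Target A, pregnancies ongoing at week 14: risk = q.
- Target B, all exposed pregnancies followed from week 4: risk = (1 − f)q.
- Planned proportion = sum over enrolment weeks of (share enrolling then) × (chance of still being ongoing at week 14) × (chance of loss in the rest of the window).

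No enrolment week contributes more than q, so the planned proportion cannot exceed target A. It can lie on either side of target B.

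**Illustration.** All inputs here are assumptions: f = 15%, q = 2%, constant weekly hazard within each period. Target A = 2.00%; target B = 0.85 × 2% = 1.70%.

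| Enrolment | Planned proportion | Ratio to A | Ratio to B |
|---|---|---|---|
| All at week 8 | 0.85^(6/10) × 2% = 1.81% | 0.91 | 1.07 |
| All at week 12 | 0.85^(2/10) × 2% = 1.94% | 0.97 | 1.14 |
| All at week 14 | 2.00% | 1.00 | 1.18 |
| All at week 16 | 1 − 0.98^(4/6) = 1.34% | 0.67 | 0.79 |
| All at week 24 | 0% | 0 | 0 |
| 50/30/20% at weeks 8/16/24 | 0.5 × 1.81 + 0.3 × 1.34 + 0 = 1.31% | 0.65 | 0.77 |

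Over f = 10 to 20% and q = 1 to 3%, the mixed pattern gives 0.64 to 0.67 of A and 0.74 to 0.80 of B. Enrolment wholly at week 12 gives 0.96 to 0.98 of A and 1.09 to 1.20 of B.

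**Network/HMO reports.** If a network captured every exposed pregnancy from week 4, its proportion would be (1 − f)q. That equals target B, but is 0.80 to 0.90 of target A, because first-trimester losses stay in the denominator.

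**Sampling error.** The largest size considered is 150 live births. At the 62% live-birth share in Section 9.5, that is 150/0.62 = 242 pregnancies. If late enrolment raised the share to an assumed 90%, it is 150/0.90 = 167. At an assumed 1% risk, 1.7 to 2.4 SABs are expected. At 5 live births (5/0.62 = 8.1 pregnancies), fewer than 0.1 are expected. Two SABs in 242 is 0.83% (exact 95% interval 0.10 to 2.95%). Removing a quarter of the denominator gives 2/182 = 1.10% (0.13 to 3.91%). The intervals overlap almost fully.

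**The case against.** **A deliberate exception.** Section 8 speaks of SAB overall and also notes that early losses may go unrecognised or unreported. That would be a sensible reason to restrict an estimate to second-trimester losses. But no exception is stated, and the 16-week example falls in the second trimester if weeks run from LMP, so the delayed-entry objection applies to the restricted estimate too.

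**Other safeguards.** Section 9.7.3 lists gestational age at enrolment as a potential subgroup, and Section 9.9 offers, if possible, a separate look by enrolment method. Sections 9.2.3 and 9.9 commit in general terms to finding current background estimates. These touch the problem, but they do not change the denominator or name an SAB reference. Detail is deferred to a SAP that is not in the supplied text and may deal with this. One therefore cannot say the analysis will be done wrongly, only that the protocol conflicts with itself.

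**Little at stake.** This stands. SAB prevalence appears in one clause of Section 9.7 and is absent from the aims, detailed methods and formulas. SABs are also individually solicited as serious adverse events (Section 11).

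**A stronger reading.** A reader might infer that the plan will understate SAB risk and hide a signal. The documents do not support that. The downward direction holds only against pregnancies ongoing at the start of the second trimester. Against all exposed pregnancies, early enrolment pushes the proportion up, because losses before enrolment drop out. Nor may one assume that network/HMO reports are free of the problem: they may avoid delayed entry, but they keep first-trimester losses in the denominator.

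**Conclusion.** The point holds and is minor. The conflict between Sections 8 and 9.7 is textual and needs no assumption. Nor does the fact that the denominator ignores enrolment week and includes women who cannot be cases. Relative to pregnancies ongoing when the second trimester opens, the bias is downward or nil. Relative to all exposed pregnancies, its direction depends on the enrolment-week mix.

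The size cannot be derived from the documents, which give neither an enrolment-week distribution nor gestation-specific loss rates. The ratios above are illustrations that also assume loss risk is unrelated to enrolment timing. With about two expected events at an assumed 1% risk, sampling error outweighs the bias in most of the scenarios shown. A reader might infer that the registry's main conclusions are at risk; they are not, since MCM, preterm birth and LBW do not use this denominator and no decision rule depends on SAB.

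**What to change.** Reconcile Section 8 with Section 9.7 in one of two ways.

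(a) Delete the second-trimester SAB prevalence and its intervals from Section 9.7. Report SAB counts with gestational week at enrolment and at loss.

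(b) Keep the estimate and:

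- amend Section 8 to state the exception and its reason;
- define the target as pregnancies ongoing at the start of the second trimester;
- settle one time origin for week 14, since Section 9.4.1 allows conception or LMP, about two weeks apart, which could shorten the window from six gestational weeks to four;
- count each consented woman at risk from the later of enrolment and window start up to week 20, so that women enrolled at week 20 or later contribute nothing;
- analyse network/HMO reports separately;
- name an SAB reference prevalence or drop the 1-sided interval.

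Under (b), the risk for the whole window can be estimated only if some women are enrolled by its start.

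The cost is wording in the protocol and the SAP. LMP, estimated delivery date, registration date, and date and gestational age at outcome are already collected. The downside is no SAB proportion under (a), or a smaller denominator and a wider interval under (b).
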